## 11. APPENDICES

### 11.1. Appendix 1 Definition and Use of Visit Windows in Reporting

Visit windows will be used for efficacy variables and for any safety data that are displayed or summarized by study visit.

Visit Label	Target Day	Analysis Visit Window
Baseline	1	Up to Day 1
Month 1	31	Days 2 to 60
Month 3	91	Days 61 to 136
Month 6	181	Days 137 to 226 but <=Day 1E
Month 9	271	Days 227 to 316 but <=Day 1E
Month 3E	91E	Days 2E to 136E
Month 6E	181E	Days 137E to 226E
Month 9E	271E	Days 227E to 316E
Month 12E	361E	Days 317E to 406E
Month 15E	451E	Day 407E to 541E
Month 21E	631E	Day 542E to 721E
Month 27E	811E	Day 722E to 901E
Month 33E	991E	Day 902E to 1081E
Month 39E	1171E	Day 1082E to 1261E
Month 45E	1351E	Day 1262E to 1441E
Month 51E	1531E	Day 1442 to last dose + 14 days
28-Day Follow-up	28 days after last dose	Based on nominal visit
6-Month Follow-up	182 days after discontinuation	Based on nominal visit

E=relative day to the first dose at active therapy extension phase.

If more than one observation falls within a visit window, the observation that is the closest to the target date for that visit will be used for the summary tables. If two visits are equally distant from the target day, the data from the later visit will be used.

Data collected in TP2, from the first dose in TP2 till the end of follow-up or the first dose in TP3, will be used to derive analysis visits in TP2. Data collected in TP3, from the first dose in TP3 or the Observation Period will be used to derive analysis visits in TP3.

Some endpoints (eg, BAEP) are not scheduled to be assessed at each visit and some measurement may fall outside the scheduled visit windows. In this case, for variables where mixed model methodology is used, the data from the unscheduled 'windowed' visits will not be included in mixed model analysis. However, these visits will be summarized descriptively in the observed cases analysis, using the visit timepoint corresponding to their actual visit window (for example a participant with a visit on Day 59 will be summarized at Month 1 in the observed case summaries).

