10.9. Appendix 9: Alternative Measures During Public Emergencies

The alternative study measures described in this section are to be followed during public emergencies, including the coronavirus disease-2019 (COVID-19) pandemic. This appendix applies for the duration of the COVID-19 pandemic globally and will become effective for other public emergencies only upon written notification from Pfizer. NOTE: Any deviations from the SoA (Section 1.3) or the protocol (eg, missed or partially completed procedures or assessments) must be reported to the Sponsor in a timely manner and will be reported by the Sponsor as a protocol deviation.

Procedures which are missed due to disruptions related to a public emergency, including the COVID-19 pandemic, are required to be performed at the next available opportunity, even if outside of a protocol-specified visit window.

Use of these alternative study measures are expected to cease upon the return of business as usual circumstances (including the lifting of any quarantines and travel bans/advisories).

In this appendix, safety assessment terms include 1) special safety assessments (audiological evaluations, including BAEP, by the audiologist, neurological evaluation by the neurologist, and the skin biopsy) and 2) usual safety assessments (all other safety evaluations).

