6	Month 9 (Day 271)	±7 days (Day 264-278)	-14/ +14 days (Day 257-285)	-14/ +60 days (Day 257-331) ^c
7	Month 3E (Day 91E)	±7 days (Day 84E-98E)	-14/ +30 days (Day 77E-121E)	NA
8	Month 6E (Day 181E)	±7 days (Day 174E-188E)	-14/ +30 days (Day 167E-211E)	NA
9	Month 9E (Day 271E)	±7 days (Day 264E-278E)	-14/ +30 days (Day 257E-301E)	-14/ +30 days (Day 257E-301E)
10	Month 12E (Day 361E)	±7 days (Day 354E-368E)	-14/ +30 days (Day 347E-391E)	NA
11	Month 15E (Day 451E)	±7 days (Day 444E-458E)	-14/ +30 days (Day 437E-481E)	-14/ +30 days (Day 437E-481E)
12	Month 21E (Day 631E)	±7 days (Day 624E-638E)	-14/ +30 days (Day 617E-661E)	NA
13	Month 27E (Day 811E)	±7 days (Day 804E-818E)	-14/ +30 days (Day 797E-841E)	-14/ +30 days (Day 797E-841E)
14	Month 33E (Day 991E)	±7 days (Day 984E-998E)	-14/ +30 days (Day 977E-1021E)	NA
15	Month 39E (Day 1171E)	±7 days (Day 1164E-1178E)	-14/ +30 days (Day 1157E-1201E)	-14/ +30 days (Day 1157E-1201E)
16	Month 45E (Day 1351E)	±7 days (Day 1344E-1358E)	-14/ +30 days (Day 1337E-1381E)	NA
17	Month 51E (Day 1531E)	±7 days (Day 1524E-1538E)	-14/ +30 days (Day 1517E-1561E)	-14/ +30 days (Day 1517E-1561E)

- a. These are the same as the windows in the protocol SoA (Section 1.3).
- b. Laboratory results must be received and reviewed by the investigator within 14 days after they are collected to determine eligibility to continue dosing. In addition, laboratory test results from the previous

Table 4. Windows for Remote Visits, Laboratory Sample Collections, and Special Safety Assessments if Required due to Public Emergencies Including COVID-19

Visit Identifier	Visit Month (Day in Study)	Remote Visit Window (Day in Study) ^a	Lab Collection Window (Day in Study) ^b	Special Safety Assessment Window (Day in Study) ^c
------------------	----------------------------	-------------------------------------------------	---------------------------------------------------	--------------------------------------------------------------

visit must be available and reviewed by the investigator prior to shipping investigational product at the current visit.

- c. The visit window for the on-site visit (Special Safety Assessments) for Month 9 is -7/+60 days and (Section 10.9.4). During TP3, the only special safety assessment is the audiological assessment.

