10.9.4. Month 9 Visit Window

The visit window for the special safety assessments at Month 9 in the setting of a public health emergency is expanded to -7 / +60 days. The usual safety assessments are to be completed as above. The full month 9 visit including the special safety assessments (audiological evaluations, neurological evaluation, and the skin biopsy) have until +60 days to be completed onsite or at the designated ancillary center. If required Special Safety Assessments (Section 10.9) cannot be performed at Month 9, the participant will not be allowed into the active therapy extension phase and must follow Early Termination procedures (Section 7.1).

Double-blind investigational product is dispensed until all the specialized safety assessments have been completed. The site staff should contact the IMPALA Help Desk for assistance.

Active therapy investigational product is dispensed only after all the special safety assessments have been completed and is the start of the extension portion of the study.

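### SAP Appendix 1 closes Month 9 at Day 316, but in a public emergency the protocol allows the Month 9 visit to Day 331, so a compliant BAEP on Days 317–331 has no analysis visit

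*SAP*

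**What the plan says.** SAP Appendix 1 applies its visit windows to efficacy variables and to safety data summarised by visit. SAP 8.1 names BAEP, skin biopsy and efficacy endpoints as by-visit tables. The Month 9 row, with target Day 271, reads "Days 227 to 316 but <=Day 1E". The next row, Month 3E, starts at Day 2E, and extension visits use only data from the first extension dose onward.

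Protocol Appendix 9 sets emergency rules. On scope it says: "This appendix applies for the duration of the COVID-19 pandemic globally". It defines "special safety assessments (audiological evaluations, including BAEP, by the audiologist, neurological evaluation by the neurologist, and the skin biopsy") as one group. For that group the Table 4 entry at Month 9 ends at "60 days (Day 257-331"), and footnote c says: "The visit window for the on-site visit (Special Safety Assessments) for Month 9 is -7/+60 days". Section 10.9.4 states that the full Month 9 visit, including these assessments, will "have until +60 days to be completed onsite or at the designated ancillary center". It adds: "Active therapy investigational product is dispensed only after all the special safety assessments have been completed". The Month 9 emergency laboratory window is shorter, ending at "14 days (Day 257-285").

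Sections 10.9.2 and 10.9.8 restrict SALT and PGI-C to on-site visits. Protocol 9.4.3 fits the primary model with Months 6 and 9 as its visits. SAP 6.3.2 treats missing PGI-C in the placebo-controlled phase as non-response.

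**The concern.** The protocol calls a recording on Day 320 a valid Month 9 assessment. The SAP has no row for that day. Month 9 I-V interwave latency is the primary endpoint, so data obtained within the protocol's own limits would leave the primary analysis because of a window boundary, with no stated decision to exclude them.

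The same applies to SALT and PGI-C from a late on-site visit. For PGI-C the effect is more than a lost record, because an unmapped responder would be counted as a non-responder. For skin biopsies, Month 9 is the only scheduled post-baseline sample in the placebo-controlled phase for participants who do not switch at Month 6 (protocol 4.1), so no other scheduled value replaces it.

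**Working it through.** **Protocol limits.** Target Day 271 (protocol schedule of activities and SAP Appendix 1).
- Upper limit: 271 + 60 = Day 331. This reproduces Table 4.
- Lower limit: 271 − 14 = Day 257 in the Table 4 cell, or 271 − 7 = Day 264 in footnote c and 10.9.4. Both sources share the upper limit.
- Routine central read and repeats: 271 + 21 = Day 292.
- Month 9 emergency laboratory limit: 271 + 14 = Day 285.

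**Unmapped days.** The SAP window ends at Day 316 (271 + 45). The protocol allows 331 − 317 + 1 = 15 further days. These precede Day 1E, because active therapy waits for the assessments, so the Month 3E row cannot take them.

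**Other BAEP visits in the emergency table.**

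| Visit | Protocol emergency window | SAP window | Covered |
|---|---|---|---|
| Month 6 | 167–211 | 137–226 | yes |
| Month 9 | 257–331 | 227–316 | no, 15 days over |
| Month 9E | 257E–301E | 227E–316E | yes |
| Month 15E | 437E–481E | 407E–541E | yes |

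**What happens to a Day 320 BAEP.** The model has levels for Months 6 and 9 only, and the record has neither label. For measurements off schedule, Appendix 1 falls back to an observed-case summary at the window in which the record lies, but no window contains Day 320. Only the two follow-up rows use the nominal visit.

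**Precision.** The planned half-width is 0.07 ms with SD 0.2 ms and 30 per group (protocol 9.2). It reproduces: 1.96 × 0.2/√30 = 0.0716 ms, or 0.0747 ms with the t quantile.

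The documents give no count of late recordings. Suppose k of 30 in an arm are lost (k assumed).
- Simple summary: t(29 − k) × 0.2/√(30 − k).
- Mixed model, approximately: t(29 − k) × 0.2 × √[(1 − r²)/(30 − k) + r²/30]. Here r is the assumed Month 6 to Month 9 correlation, all 30 have a Month 6 value, and the SD is the same at both visits.

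| k lost | Simple summary (ms) | Mixed model, r = 0.5 (ms) | Mixed model, r = 0.8 (ms) |
|---|---|---|---|
| 0 | 0.0747 | 0.0747 | 0.0747 |
| 1 | 0.0761 (+1.9%) | 0.0758 (+1.4%) | 0.0753 (+0.8%) |
| 3 | 0.0791 (+5.9%) | 0.0781 (+4.6%) | 0.0765 (+2.5%) |
| 6 | 0.0845 (+13.1%) | 0.0823 (+10.2%) | 0.0789 (+5.6%) |

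**PGI-C.** With 30 per arm, each unmapped responder counted as a non-responder lowers that arm's Month 9 rate by 1/30 = 3.3 percentage points.

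**The case against.** The day count is hard to dispute. The case on the other side concerns reach and importance.

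- **Rarity.** The gap needs an emergency and an assessment 46 to 60 days late. Routine conduct ends at Day 292, inside the window. This stands. The losses of 1 to 6 per arm used above have no documentary basis.
- **Existing safeguards.** SAP 6.7 plans COVID-19 deviation listings, a missed-visit summary for latency, and subject listings. These make late data visible but do not return a value to the model.
- **Late recordings are arguably not Month 9.** A limit of 45 days past target is defensible as an analysis choice. However, the SAP gives no reason for discarding values that the protocol accepts as Month 9. SAP Appendix 3 also runs the Month 9 compliance period to the day before Day 1E.
- **Biopsy.** SAP 6.2.2 and 6.2.3 use a 'Month 9/EOP' timepoint, and 6.2.2 defines EOP by phase. Month 6 switchers have their biopsy at Month 6 instead of Month 9, so day windows alone cannot produce that timepoint. A reader might infer that a late biopsy is certainly lost. The documents do not settle this: Appendix 1 has no EOP row, yet the label could be read to include the biopsy.
- **Treatment status.** A reader might also infer that these recordings are off treatment. Protocol 6.2.1 limits extra double-blind dosing to the +21-day window, 10.9.5 bars additional supply to extend a visit window, and 10.9.4 continues double-blind supply until the assessments are done. These passages must be reconciled, but they do not alter the Day 331 limit.

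**Conclusion.** The mismatch is real, and it affects the primary endpoint. Fifteen protocol-permitted days, 317 to 331, have no analysis visit. A BAEP on those days leaves the primary model and cannot be placed in the observed-case summary. On the wording of 10.9.4, on-site SALT and PGI-C from a late visit are unmapped in the same way. The biopsy is probably affected, with the ambiguity described above.

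A reader might infer that primary data were actually lost or that the reported result is unreliable. The documents do not support that: no count is given, and it may be zero. The likely effect on BAEP precision is small, at most about 10% in half-width under the mixed-model assumptions shown (six of 30 lost, correlation 0.5). No hypothesis is tested. The point is still worth fixing, because a written rule discards compliant data and changing it costs little.

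**What to change.** In SAP Appendix 1, change the Month 9 row to Days 227 to 331, still capped at Day 1E, for all Month 9 assessments. Leaving SALT and PGI-C at Day 316 would keep the same gap for them. Emergency laboratory data end at Day 285 and already fit. State that the Month 9/EOP biopsy is the last one before active therapy.

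Report by arm how many BAEP, biopsy, SALT and PGI-C records fall on Days 317–331. Use the corrected window in supplemental CSR 1. SAP Table 1 describes analyses as already added to the PCD report, so the primary analysis appears to be done. Show the rerun Month 9 analyses with and without these records as a labelled sensitivity analysis.

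The cost is one changed row, one sentence, a count and a rerun. On-time records are not displaced, because Appendix 1 keeps the observation closest to target. The small downside is that late records reflect up to 60 more days in the placebo-controlled phase, against up to 45 under the present window.

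Separately, the protocol should reconcile 6.2.1, 10.9.4 and 10.9.5 on continued double-blind supply, and the −14 versus −7 day lower limit between the Table 4 cell and its footnote and 10.9.4. Neither changes the Day 331 limit.

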10.7.1. Monitoring

All potential treatment-related events of rash will be followed up until resolution or agreement with Pfizer.

The following laboratory abnormalities require re-testing until resolution or agreement with Pfizer:

Table 3. Laboratory Retesting Criteria

Laboratory Variable	Laboratory Value	Re-testing Timeframe ^a
Hematology		
Absolute Neutrophil Count	<1000/mm ³ (<1.0 × 10 ⁹ /L)	Within 1 week
Hemoglobin	<10.0 g/dL (<6.21 mmol/L or <100 g/L)	Within 1 week
Platelet count	<100,000/mm ³ (<100 × 10 ⁹ /L)	Within 1 week
Absolute Lymphocyte Count ^b	<600/mm ³ (<0.6 × 10 ⁹ /L)	Within 1 week
Serum Chemistry		
Creatine kinase ^c	>3 × ULN	Within 1 week
Aspartate aminotransferase	See Section 10.5 for potential cases of drug-induced liver injury.	Within 48 hours
Alanine aminotransferase	See Section 10.5 for potential cases of drug-induced liver injury.	Within 48 hours
Total bilirubin	See Section 10.5 for potential cases of drug-induced liver injury.	Within 48 hours

a. Based on awareness of the abnormal result.

b. Participants with absolute lymphocyte count <500/mm³ (0.5 × 10⁹/L) will be reflex-tested for FACS-TBNK until the absolute lymphocyte count resolves or stabilizes at a level acceptable to the investigator and sponsor.

c. In addition to re-testing creatine kinase >3× ULN, urine myoglobin will be performed as reflex testing for any participant with creatine kinase >10× ULN for visits on or before Month 15E. For participants who have completed the Month 15E Visit, creatine kinase and urine myoglobin will not be tested.

In case of positive urine pregnancy test, the participant will have study intervention interrupted and a serum sample collected on the same day (or as soon as possible) and submitted to the central laboratory for pregnancy testing.

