 - $>3 \times$ ULN with at least one total bilirubin value $>2 \times$ ULN;
 - $>3 \times$ ULN accompanied by signs or symptoms consistent with hepatic injury (eg, new onset elevated PT/INR);
 - Two sequential AST or ALT elevations $>5 \times$ ULN, regardless of total bilirubin or accompanying signs or symptoms.

NOTE: In each case, there is a need for additional investigations, such as review of ethanol, recreational drug, and dietary supplement consumption; testing for acute hepatitis A, B or C infection and biliary tract imaging should be promptly discussed with the sponsor or designee.

Pregnancy:

Female participants confirmed as pregnant during the study (see [Section 8.3.5](#)).

Prohibited Medications:

- Participants who are treated with any prohibited medication during the course of the study may require discontinuation. Participants who are administered a prohibited medication should be discussed with the sponsor for possible withdrawal from the study.

Suicidal Ideation:

- Participants with suicidal ideation associated with actual intent and a method or plan in the past year: a “yes” answer on items 4, 5, or on any question in the suicidal behavior section of the C-SSRS must be discontinued. The participant must be

referred to a mental health professional for appropriate evaluation and treatment or immediately referred to the Emergency Room at the investigator's judgement.

Discontinuation/End of Treatment Monitoring:

- Any participant meeting discontinuation criteria must enter into the Follow-up Period with their first follow-up visit occurring 1 week after their last dose whenever possible, until the event has returned to normal or baseline levels or is deemed clinically stable. The procedures scheduled for Early Termination Visit will be performed on the last day the participant takes the study intervention or as soon as possible thereafter. The only exception to this is when a participant specifically withdraws consent for any further contact with him or her or persons previously authorized by the participant to provide this information. Additional follow-up visits may occur as needed until any clinically relevant abnormalities or adverse events have resolved, returned to a baseline state, or are deemed clinically stable.

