#### **6.7. Safety Summaries and Analyses**

Safety analysis will be based on the safety population.

Analyses for the primary and secondary safety endpoints are discussed in [Section 6.1](#) and [Section 6.2](#).

In general, safety data will be presented in tabular and/or graphical format and summarized descriptively, where appropriate. All safety endpoints will be listed and summarized in accordance with Pfizer Standards. Categorical outcomes (eg, AEs) will be summarized by subject counts and percentage. Continuous outcome (eg, blood pressure, pulse rate, etc.) will be summarized using N, mean, median, standard deviation, etc. Change from baseline in laboratory data, ECGs and vital signs will also be summarized. Subject listings will be produced for these safety endpoints accordingly. Clinically significant abnormalities in vital signs and clinical laboratory values are discussed in [Sections 6.2.9](#) and [6.2.10](#).

In order to report the impact of COVID-19 on clinical trial populations and study data, additional listings and summaries will be produced:

- Protocol deviations related to COVID-19
- Summary of discontinuations due to COVID-19 related reasons
- Discontinuation from study/study drug interruptions due to COVID-19 related adverse events
- COVID-19 related adverse events
- Number of days with missed doses due to COVID-19
- Missed visits summary for I-V interval latency on BAEP

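### SAP Appendix 1 gives scheduled laboratory samples no priority within a visit window, so a re-test prompted by an abnormal result, or an off-drug test, can replace the scheduled value in by-visit summaries

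*SAP*

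**What the plan says.** **Scope.** SAP 11.1 (Appendix 1) states: "Visit windows will be used for efficacy variables and for any safety data that are displayed or summarized by study visit". SAP 6.7 adds: "Change from baseline in laboratory data, ECGs and vital signs will also be summarized".

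**Choice among several records.** Within a window, "the observation that is the closest to the target date for that visit will be used for the summary tables". The tie rule is: "If two visits are equally distant from the target day, the data from the later visit will be used". The one exclusion of unscheduled records concerns models: "the data from the unscheduled 'windowed' visits will not be included in mixed model analysis". The same paragraph keeps those records in the observed-case summaries.

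**Limit relative to last dose.** Only the Month 51E row has one: "Day 1442 to last dose + 14 days". TP2 windows accept data up to the end of follow-up or the first TP3 dose. The 28-Day and 6-Month Follow-up visits keep their nominal labels.

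**Where extra samples come from.**
- Protocol 10.7.1: "The following laboratory abnormalities require re-testing until resolution or agreement with Pfizer". Table 3 sets 1 week for hematology and creatine kinase and 48 hours for liver tests, counted from awareness of the result.
- Protocol 8.2.10: clinically significant abnormal values, including those within 28 days of last dose, are repeated until normal, back at baseline or no longer significant.
- Protocol 10.7.2: participants meeting a discontinuation criterion enter follow-up, with the "first follow-up visit occurring 1 week after their last dose whenever possible". That visit has no row in Appendix 1.

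**The concern.** Nearest-to-target selection is harmless when extra records arise independently of the result. Here many do not. A listed abnormality triggers a repeat, and repeats stop once the value has settled. A rule that is blind to why a sample was taken can therefore show the recovered value under the visit label and drop the abnormal one. The same rule can place a test taken after stopping drug under an on-treatment visit.

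This is a safety study with about 30 participants per arm, so one displaced extreme can change a by-visit minimum or maximum. If one arm has more abnormalities, it will have more re-tests and more replacements.

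**Working it through.** The plan gives no figure to reproduce, so the check enumerates the SAP rule.

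**1. Condition for replacement.** Let the scheduled sample fall s days from target and the re-test L days later. The re-test is used if |s + L| ≤ |s|. This requires s < 0 and L ≤ 2|s|. At s = −7 any lag of 1 to 14 days qualifies; at s = −3, lags of 1 to 6; at s = −1, lags of 1 to 2; at s ≥ 0, none.

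**2. Share of positions, ±7-day visits.** The ±7-day window is from the protocol's Schedule of Activities. Assumptions: s is uniform over its 15 values, and L is as shown (the documents give no distribution).

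| Lag L (days) | s that qualify | Share |
|---|---|---|
| 2 | −7 to −1 | 7/15 = 47% |
| 3 | −7 to −2 | 6/15 = 40% |
| 5 | −7 to −3 | 5/15 = 33% |
| 7 | −7 to −4 | 4/15 = 27% |
| 10 | −7 to −5 | 3/15 = 20% |

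Ties occur only at even lags and supply one position in 15 (7 percentage points). Closest-to-target selection does most of the work.

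**3. Month 1 (±3 days).** The same count over 7 positions gives 3/7 = 43% at L = 2, 2/7 = 29% at L = 3, 1/7 = 14% at L = 5, and 0 at L = 7 or 10.

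**4. Re-test example (values assumed).** Month 6 has target Day 181. A Day 176 creatine kinase of 5×ULN is 5 days away; a Day 183 re-test at 1×ULN is 2 days away. Month 6 becomes 1×ULN. In an arm of 30 the mean falls by (5 − 1)/30 = 0.13×ULN, and if the 5×ULN was the arm maximum, that maximum is lost.

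**5. Off-drug example.** Drug is stopped and the ET sample taken on Day 150; a test follows on Day 157. Both lie in the Month 6 window (Days 137 to 226). Distances to Day 181 are 31 and 24 days, so the off-drug value becomes Month 6 and the ET value drops out. Day 157 is 7 days after last dose, so a 14-day limit like the one at Month 51E would not prevent this.

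Counting ET days 2 to 270 with a test exactly 7 days later in the same window and at least as close to target:
- Month 1, Days 2–27: 26
- Month 3, Days 61–87: 27
- Month 6, Days 137–177: 41
- Month 9, Days 227–267: 41

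The total is 135 of 269, or 50%. This assumes uniform stopping days, ET on the day of last dose, and a laboratory test exactly 7 days later.

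**6. Effect on a mean.** Shift = (share re-tested) × (share replaced) × (recovery in SD). With assumed ranges of 2–10%, 10–30% and 0.5–2 SD:
- lowest: 0.02 × 0.10 × 0.5 = 0.001 SD
- highest: 0.10 × 0.30 × 2 = 0.06 SD
- at the largest share in step 2: 0.10 × 0.47 × 2 = 0.094 SD

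The standard error of a mean of 30 is 1/√30 = 0.18 SD.

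**The case against.** **By-visit laboratory tables are implied, not listed.** SAP 6.7.3 and 6.7.4 call for by-visit summaries of vital signs and ECG; SAP 6.7.2 does not say so for laboratory data and defers to sponsor standards, which might handle repeats. This stands as a limit on certainty. Change from baseline in laboratory data is nonetheless planned, and Appendix 1 covers any safety data shown by visit.

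**The selection is not strictly one-way.** A reader might infer that normal results are never re-tested and so never replaced. The documents do not support that: protocol sections 8, 8.2 and 8.2.10 allow unscheduled tests for any perceived safety issue and repeats for technical reasons. A re-test can also confirm or worsen a finding; the laboratory discontinuation criteria in 10.7.2 require such confirmation. The pull toward normal is a tendency that follows from why most repeats are ordered and when they stop.

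**Short lags may be uncommon.** Samples go to a central laboratory and the re-test clock starts at awareness, so the 47% at 2 days is the favourable end for replacement. This stands.

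**The off-drug case is narrow.** The 1-week visit applies to participants meeting discontinuation criteria, is asked for only where possible, and has no listed laboratory panel. ET itself may fall up to 7 days late. In the Day 150 example no scheduled Month 6 sample exists, so an ET value is displaced. The 50% is therefore illustrative.

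**Little depends on it.** No hypothesis is tested, listings retain the values, and the secondary laboratory endpoint is an incidence. This is correct and fixes the point as minor.

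**Conclusion.** The point holds as a minor gap in the plan. Appendix 1, read with the protocol's re-test and follow-up rules, allows an abnormal on-drug laboratory value to be replaced by a recovered or off-drug one in descriptive by-visit summaries. Replacement is conditional on the scheduled or ET sample preceding the target day. For re-tests at ±7-day visits, the 20% to 47% range rests on uniform visit timing and assumed lags of 10 to 2 days.

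The likely direction is toward normal, with minima and maxima more exposed than means. The mean shift is about 0.001 to 0.06 SD under the stated assumptions, well inside a standard error of 0.18 SD.

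A reader might infer that the drug's laboratory effect will be materially understated in the reports. The documents do not support that: they give no re-test frequency or recovery size, and the tables of laboratory abnormalities and discontinuation criteria are grouped by period (SAP 6.7.2, 8.1, 8.2), so the window rule does not touch them.

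**What to change.** Add to SAP Appendix 1, in substance:
- Descriptive by-visit laboratory summaries use the scheduled (or ET) assessment. An unscheduled or repeat assessment is used only if no valid scheduled result exists in the window, for example because the sample was technically invalid.
- Unscheduled assessments after the last dose are not assigned to on-treatment visits.
- All records remain in the incidence and criteria tables and in the listings.

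The validity exception ensures that a flawed scheduled sample is not preferred to its technical repeat. Extending the 14-day limit alone would not be enough, as the Day 157 example shows.

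The cost is a few SAP sentences and a priority flag in the windowing program. A few repeat values would move from by-visit tables to listings. The SAP version history speaks of the PCD CSR in the past tense, so TP1 may already have been reported under the present rule; later reports should note any difference from its by-visit tables.
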